6.6.1.1. Dose Modification Guidance due to Toxicities Considered to be Attributed to Abemaciclib

Abemaciclib hematological toxicities may overlap with those of chemotherapy. To aid in appropriately attributing hematological toxicities to abemaciclib, below is a description based on adult Phase 3 registration studies (MONARCH 2 [Sledge et al. 2017]; MONARCH 3 [Goetz et al. 2017; Johnston et al. 2019]):

- The TEAE of neutropenia was the most frequent hematological toxicity reported and was predominantly of low-grade severity and not associated with severe infection. Febrile neutropenia was infrequent.
- Neutropenia was observed early in the treatment course, within the first 2 months, and maintained over the course of treatment.
- On central laboratory analysis, neutrophil count decrease from the baseline visit was observed; mean neutrophil counts generally remained stable at the later visits and were reversible once patients discontinued from treatment.
- Anemia and thrombocytopenia were reported but were less frequent than neutropenia and mostly of low-grade severity.

See Section 6.6.1.3 dose modification tables for guidance specific to Part C.

Parts A and B: Dose modification guidance is outlined below for hematologic toxicities considered to be attributed to abemaciclib:

Toxicity Type	Toxicity Profile and Severity	Abemaciclib Dose Suspension	Abemaciclib Dose Reduction
Neutropenia	Initial incidence	Dose MUST be suspended until ANC $\geq 750/\text{mm}^3$	Dose MAY be reduced at the investigator's discretion Consider addition of G-CSF at the investigator's discretion according to ASCO/ESMO guidelines (Crawford et al. 2010; Smith et al. 2015)
	If lasting >7 days or causing cycle delay of >14 days	Suspend abemaciclib until ANC $\geq 750/\text{mm}^3$	Dose MUST be reduced by 1 dose level.
	Subsequent incidences	Suspend abemaciclib until ANC $\geq 750/\text{mm}^3$	Dose MUST be reduced by 1 dose level.
Thrombocytopenia	Initial incidence	Dose MUST be suspended until platelets $\geq 75,000/\text{mm}^3$	Dose MAY be reduced at the investigator's discretion.
	If lasting >7 days or causing cycle delay of >14 days	Dose MUST be suspended until platelets $\geq 75,000/\text{mm}^3$	Dose MUST be reduced by 1 dose level.
	Subsequent incidences	Dose MUST be suspended until platelets $\geq 75,000/\text{mm}^3$	Dose MUST be reduced by 1 dose level.

Toxicity Type	Toxicity Profile and Severity	Abemaciclib Dose Suspension	Abemaciclib Dose Reduction
Febrile neutropenia	Grade 3	Dose MUST be suspended until toxicity resolves.	Dose MAY be reduced by 1 dose level at the investigator's discretion.
	Recurrent Grade 3 ^a	Dose MUST be suspended until toxicity resolves.	Dose MUST be reduced by 1 dose level.
	Grade 4	Dose MUST be suspended until toxicity resolves.	Dose MUST be reduced by 1 dose level.

Abbreviations: ANC = absolute neutrophil count; ASCO = American Society of Clinical Oncology; CRP/CRS = clinical research physician/clinical research scientist; ESMO = European Society for Medical Oncology; G-CSF = granulocyte-colony stimulating factor.

^a Recurrent toxicity refers to the same event occurring within the next 8 weeks (as measured from the stop date of the preceding event).

Parts A and B: The table below presents guidance for abemaciclib dose adjustments and suspensions due to nonhematologic toxicity considered to be attributed to abemaciclib.

Toxicity Type	Toxicity Profile and Severity	Abemaciclib Dose Suspension	Abemaciclib Dose Reduction
Nonhematologic Toxicity ^a (except diarrhea, ALT/AST increased, and ILD/pneumonitis)	Persistent or recurrent ^b Grade 2 that does not resolve with maximal supportive measures within 7 days to baseline or Grade 1 unless deemed clinically insignificant by the investigator	Dose MUST be suspended until toxicity resolves to either baseline or \leq Grade 1.	Dose MUST be reduced by 1 dose level.
	Grade 3 or 4	Dose MUST be suspended until toxicity resolves to either baseline or \leq Grade 1.	Dose MUST be reduced by 1 dose level.
Diarrhea ^c	Grade 2 that does not resolve within 24 hours to \leq Grade 1	Dose MUST be suspended until toxicity resolves to \leq Grade 1.	Dose MAY be reduced by 1 dose level.
	Grade 2 that persists or recurs ^b after resuming the same dose despite maximal supportive measures	Dose MUST be suspended until toxicity resolves to \leq Grade 1.	Dose MUST be reduced by 1 dose level.

Toxicity Type	Toxicity Profile and Severity	Abemaciclib Dose Suspension	Abemaciclib Dose Reduction
	Grade 3 or 4	Dose MUST be suspended until toxicity resolves to \leq Grade 1.	Dose MUST be reduced by 1 dose level.
	Any grade that requires hospitalization	Dose MUST be suspended until toxicity resolves to \leq Grade 1.	Dose MUST be reduced by 1 dose level.
ALT/AST Increased	Persistent or recurrent ^b Grade 2 ($>3.0\text{-}5.0\times$ ULN), or Grade 3 ($>5.0\text{-}20.0\times$ ULN) ^d	Dose MUST be suspended until toxicity resolves to baseline or Grade 1.	Dose MUST be reduced by 1 dose level.
	Grade 4 ($>20.0\times$ ULN)	Abemaciclib treatment MUST be discontinued	Abemaciclib treatment MUST be discontinued
ALT/AST Increased with increased total bilirubin, in the absence of cholestasis	ALT/AST $>3.0\times$ ULN with total bilirubin $>2\times$ ULN	Abemaciclib treatment MUST be discontinued.	Abemaciclib treatment MUST be discontinued.
ILD / pneumonitis	Grade 2 that persists ^b or recurs despite maximal supportive measures and does not return to baseline or Grade 1 within 7 days	Dose MUST be suspended until toxicity resolves to either baseline or \leq Grade 1.	Dose MUST be reduced by 1 dose level.
	Grade 3 or 4 (severe ILD/pneumonitis)	Abemaciclib treatment MUST be discontinued.	Abemaciclib treatment MUST be discontinued.

Abbreviations: ALT = alanine aminotransferase; AST = aspartate aminotransferase; ILD = interstitial lung disease; ULN = upper limit of normal.

- ^a Additional guidance for hepatic and renal monitoring is in Section 8.2.1.1 and Section 8.2.1.2.
- ^b Determination of persistent events will be at the discretion of the investigator. Recurrent toxicity refers to the same event occurring within the next 8 weeks (as measured from the stop date of the preceding event).
- ^c Diarrhea is a known overlapping toxicity of abemaciclib and irinotecan. This guidance is for diarrhea attributed to abemaciclib. Irinotecan has been reported to cause acute/cholinergic diarrhea and late diarrhea (>24 hours post-infusion). Refer to the label and institutional practice for dose modifications for diarrhea attributed to irinotecan. See Section 6.5.2 for descriptions of descriptions of irinotecan-induced and abemaciclib-induced diarrhea and supportive management.
- ^d Grade ≥ 3 ALT increased is a trigger for additional assessments and possibly hepatic monitoring. See Section 8.2.1.1 for additional guidance for hepatic monitoring.

6.6.1.2. Dose Modification Guidance due to Toxicities Considered to be Attributed to Irinotecan

For individuals receiving irinotecan who experience elevated bilirubin or impaired glucuronidation, the following guidance is suggested for all study Parts:

- Elevated bilirubin: For patients with bilirubin ranging from 1.5 to 3 times the ULN, a reduced dose of irinotecan should be considered. For patients with bilirubin beyond 3 times the ULN, irinotecan should not be used.
- Impaired glucuronidation: Patients known to have reduced UGT1A1 activity (whether preexistent substance-induced, disease-induced, due to an inherited disorder [e.g. Gilbert syndrome, Crigler-Najjar syndrome], or induced by trial therapy) may have increased risk of hematological toxicity and/or diarrhea. These participants should be carefully monitored for hematologic toxicities and diarrhea. A reduced irinotecan starting dose should be considered for patients who have experienced prior hematologic toxicity or significant diarrhea with previous treatment.
- For Grade 4 therapy-related diarrhea that develops despite maximal anti-diarrhea medications and prophylactic antibiotics, reduce irinotecan by 25% (i.e., 37.5 mg/m²/dose) in subsequent cycles.

See Section 6.6.1.3 dose modification tables for guidance specific to Part C.

Grade 3 Diarrhea		Hold until ≤Grade 1, then reduce dose	Hold until ≤Grade 1, may reduce 25%	No change	No change
Grade 4 Diarrhea	1 st Event	Hold until ≤Grade 1, then reduce dose	Hold until ≤Grade 1, reduce 25%	No change	No change
	Recurs despite abemaciclib reduction	Hold until ≤Grade 1, then reduce dose	Hold until ≤Grade 1, reduce 50%	No change	No change
	Recurs despite abemaciclib and irinotecan reduction	Hold until ≤Grade 1, then resume reduced dose	Hold until ≤Grade 1, then resume reduced dose	No change	Reduce to 13.13 mg/m ² /dose
	Recurs despite maximum dose reductions	Discontinue all study drugs			

^a Determination of persistent events will be at the discretion of the investigator. Recurrent toxicity refers to the same event occurring within the next 8 weeks (as measured from the stop date of the preceding event).

Part C Dose Modifications for Vomiting and Dehydration					
		Abemaciclib	Irinotecan	Temozolomide	Dinutuximab
Vomiting Despite Maximum Supportive Care	Persistent or recurrent ^a Grade 2 that does not resolve within 7 days to baseline or Grade 1	Hold until ≤Grade 1, then reduce dose	No change	No change	No change
	Grade 3	Hold until ≤Grade 1, then reduce dose	No change	No change	No change
	Grade 4: 1 st Event	Hold until ≤Grade 1, then reduce dose	Reduce 25%	Reduce 25%	No change
	Grade 4: Recurs despite supportive care and dose reductions	Discontinue all study drugs			
≥ Grade 3 Dehydration Persisting > 3 Days Not Associated with Vomiting or Diarrhea	1 st Event	No change	Reduce 25%	Reduce 25%	No change
	Recurs despite dose reductions	Discontinue all study drugs			

^a Determination of persistent events will be at the discretion of the investigator. Recurrent toxicity refers to the same event occurring within the next 8 weeks (as measured from the stop date of the preceding event).

Part C Dose Modifications for Hepatotoxicity						
		Abemaciclib	Irinotecan	Temozolomide	Dinutuximab	
Elevated Bilirubin	1.5-3x ULN	No change	Hold until \leq Grade 1, may reduce	No change	No change	
	$>3x$ ULN	Discontinue all study drugs				
Persistent or Recurrent ^a Grade 2 AST/ALT Increase	Persistent or recurrent	Hold until \leq Grade 1, then reduce dose	No change	No change	No change	
Grade 3 AST or ALT Increase ^a	\leq 7 days	Hold until \leq Grade 1, then reduce dose	No change	No change	No change	
	Persists >7 days	Hold until \leq Grade 1, then reduce dose	No change	No change	Reduce to 13.13 mg/m ² /dose	
	Recurrent despite reductions	Hold until \leq Grade 1, then reduce dose	No change	No change	Reduce to 8.75 mg/m ² /dose	
Grade 4 ($>20x$ ULN AST or ALT) Any Duration ^b	1 st Event	Discontinue all study drugs				
ALT Increase (Any Grade) Causing Cycle Delay >14 days ^{b,c}	1 st Event	Modify per Section 6.6.1.1	No change	No change	Reduce to 13.13 mg/m ² /dose	
	Recurs despite dinutuximab dose reduction	Discontinue all study drugs				

Abbreviations: ALT = alanine aminotransferase; AST = aspartate aminotransferase; ULN = upper limit of normal.

^a Determination of persistent events will be at the discretion of the investigator. Recurrent toxicity refers to the same event occurring within the next 8 weeks (as measured from the stop date of the preceding event).

^b Grade ≥ 3 ALT increased is a trigger for additional assessments and possibly hepatic monitoring. See Section 8.2.1.1 for additional guidance for hepatic monitoring.

^c Delay of >14 days indicates more than 35 days from Day 1 of previous cycle.

Part C Dose Modifications for Miscellaneous Toxicity					
		Abemaciclib	Irinotecan	Temozolomide	Dinutuximab
ILD or Pneumonitis	Persistent or recurrent ^a Grade 2 despite maximal supportive care ^b	Hold until \leq Grade 1 then reduce dose	Hold until \leq Grade 1 then reduce dose	No change	No change
	Grade 3 or 4	Discontinue all study drugs			
Nonhematologic Toxicity not Otherwise Described Above	Grade 2 Persistent or recurrent ^{a, b}	Hold until \leq Grade 1 then reduce dose	No change	No change	No change
	Grade 3 or 4	Hold until \leq Grade 1 then reduce dose	Hold until \leq Grade 1 then reduce dose	Hold until \leq Grade 1 then reduce dose	No change
Any AE-Associated Cycle Delay of >21 Days^c	1 st Event	Discontinue all study drugs			

Abbreviations: AE = adverse event; ILD = interstitial lung disease.

- ^a Determination of persistent events will be at the discretion of the investigator. Recurrent toxicity refers to the same event occurring within the next 8 weeks (as measured from the stop date of the preceding event).
- ^b Does not resolve with maximal supportive measures within 7 days to baseline or Grade 1 unless deemed clinically insignificant by the investigator.
- ^c Delay of >21 days indicates more than 42 days from Day 1 of previous cycle. Exceptional circumstances may be allowed upon approval by CRP/CRS.

6.6.1.4. Part C-Specific Dose Modification Guidance due to Toxicity Attributed to GM-CSF

White blood cell (WBC) count elevation

- If total WBC count is $>50,000/\mu\text{L}$, hold GM-CSF.
- When WBC count returns to $<20,000/\mu\text{L}$, resume GM-CSF at 50% of dose.
- In subsequent cycles, use full dose of GM-CSF, but adjust dose again if the WBC count $>50,000/\mu\text{L}$.

Localized skin reaction

- GM-CSF can be continued when skin reactions are localized and mild.
- Rotation of injection sites is recommended.
- Use of IV infusion, insuflon, or other subcutaneous injection port is not recommended.
- If \geq Grade 3 injection site reaction occurs, permanently discontinue GM-CSF.

First-dose reaction

A syndrome characterized by respiratory distress, hypoxia, flushing, hypotension, syncope, and/or tachycardia has been reported following the administration of the first dose of GM-CSF within a cycle. This generally resolves with symptomatic treatment and does not recur in the same cycle.

- If “first dose reaction” occurs, reduce the next GM-CSF dose to 50%.
- If a similar reaction occurs at the 50% dose, permanently discontinue GM-CSF.
- If the 50% does not cause recurrent symptoms, escalate subsequent doses to 100%.
 - If there are recurrent severe symptoms, then all future doses will be reduced to 50% without any further attempts to escalate.
 - If 50% is tolerated, that dose should be administered for all subsequent protocol treatment for that patient.

6.7. Intervention after the End of the Study

The end of study definition is provided in Section 4.4. Investigators will continue to follow the SoA (Section 1.3) until notified by Lilly that the end of study has occurred.

6.7.1. Treatment after Study Completion

Study completion will occur following the final analysis of primary and secondary objectives, as determined by Lilly. Investigators will continue to follow the SoA (Section 1.3) for all patients until notified by Lilly that study completion has occurred.

6.7.1.1. Continued Access

Participants who are still on study intervention at the time of study completion may continue to receive study intervention if they are experiencing clinical benefit and no undue risks. The continued access period will apply to this study only if at least 1 participant is still on study intervention when study completion occurs. Lilly will notify investigators when the continued access period begins. Lilly may allow patients to enroll in a “rollover” protocol to provide long-term continued access for patients enrolled in this study.

Participants or their legal representatives are not required to sign a new ICF/assent (as applicable) before treatment is provided during the continued access period; the initial ICF/assent (as applicable) for this study includes continued access under this protocol.

The participant’s continued access to study intervention will end when a criterion for discontinuation is met (Section 7). Continued access follow-up will begin when the participant or legal representative, if applicable, and the investigator agree to discontinue study intervention and lasts approximately 30 days. Follow-up procedures will be performed as shown in the Continued Access Schedule of Activities (Section 1.3).

During the continued access period, all AEs and SAEs will be reported on the CRF. Serious adverse events will also be reported to Lilly Global Patient Safety (see Section 8.3). In the event that an SAE occurs, Lilly may request additional information (such as local laboratory results, concomitant medications, and hospitalizations) in order to evaluate the reported SAE.

Investigators will perform any other standard procedures and tests needed to treat and evaluate patients; however, the choice and timing of the tests will be at the investigator’s discretion. Lilly will not routinely collect the results of these assessments.

Participants who are in short-term follow-up when the continued access period begins will continue in short-term follow-up until the 30-day short-term follow-up visit is completed.

In all cases, no follow-up procedures will be performed for a participant who withdraws informed consent/assent unless he or she has explicitly provided permission and consent/assent.

7. Discontinuation of Study Intervention and Participant Discontinuation/Withdrawal

7.1. Discontinuation of Study Intervention

If a clinically significant finding is identified after enrollment, the investigator or qualified designee will determine if the participant can continue in the study and if any change in participant management is needed. Any new clinically relevant finding should be reported as an AE.

Possible reasons leading to permanent discontinuation of investigational product:

- the participant or the participant's designee, for example, parents or legal guardian, requests to discontinue investigational product.
- progressive disease
- cycle delay >21 days due to study drug-related AEs, unless an exception has been granted upon consultation with the Lilly CRP/CRS for an exceptional circumstance
- the patient becomes pregnant during the study
- the patient is significantly noncompliant with study procedures and/or treatment
- enrollment in any other clinical trial involving an investigational product or enrollment in any other type of medical research judged not to be scientifically or medically compatible with this study
- sponsor or investigator decision
- the patient, for any reason, requires treatment from another therapeutic agent that has been demonstrated to be effective for treatment of the study indication. Discontinuation from abemaciclib will occur prior to introduction of the new agent
- the patient experiences unacceptable toxicity

Participants discontinuing from the investigational product prematurely for any reason should complete AE and other follow-up procedures per Section 1.3 (SoA), Section 8.3 (Adverse Events and Serious Adverse Events), and Section 8.2 (Safety Assessments) of the protocol.

7.2. Participant Discontinuation/Withdrawal from the Study

Participants will be discontinued in the following circumstances:

- enrollment in any other clinical study involving an investigational product or enrollment in any other type of medical research judged not to be scientifically or medically compatible with this study
- participation in the study needs to be stopped for medical, safety, regulatory, or other reasons consistent with applicable laws, regulations, and good clinical practice (GCP)
- participant decision
 - the participant or the patient's designee, for example, parents or legal guardian requests to be withdrawn from the study

Participants discontinuing from the study prematurely for any reason should complete AE and other safety follow-up per Section 1.3 (SoA), Section 8.3 (Adverse Events and Serious Adverse Events), and Section 8.2 (Safety Assessments) of this protocol.

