Relative Day within Cycle	Begins when the patient and the investigator agree that the patient will no longer continue study treatment and lasts approximately 30 days.	Begins when short-term follow-up period is complete and continues until death, study withdrawal, or the patient is lost to follow-up. In all cases, no follow-up procedures will be performed for a patient who withdraws consent/assent unless he or she has explicitly provided permission and consent/assent.	
Clinically directed physical examination	X		Evaluations per examiner's discretion and patients' symptoms
Vital signs	X		Includes height, weight, blood pressure, pulse, temperature, and respiratory rate
Performance status	X		
 • Lansky for age <16 years • Karnofsky for age ≥16 years For patients who turn 16 years old while on study, Karnofsky should be used after the 16 th birthday

CCI

Part C			
	Short-Term Follow-Up (30±7 Days)	Long-Term Follow-Up (90±14 Days)	Comments
Visit	801	802-X	
Relative Day within Cycle	Begins when the patient and the investigator agree that the patient will no longer continue study treatment and lasts approximately 30 days.	Begins when short-term follow-up period is complete and continues until death, study withdrawal, or the patient is lost to follow-up. In all cases, no follow-up procedures will be performed for a patient who withdraws consent/assent unless he or she has explicitly provided permission and consent/assent.	
Tumor restaging evaluation CT or MRI and MIBG or PET CT	X	X	
 • Use same modality throughout the study • PET CT only for patients with non-MIBG avid lesions • Not required if PD is documented while on treatment, or if staging has been performed within the past 3 weeks • Perform during every long-term follow-up visit if PD has not occurred • Scans will be performed and reviewed locally
Adverse events collection/CTCAE grading	X	X	
 • CTCAE Version 5.0 • After Visit 801, only study treatment-related serious events are reported
Concomitant medication	X		
Hematology	X		
 • Local testing • See Section 10.2, Appendix 2
Clinical chemistry	X		
 • Local testing • See Section 10.2, Appendix 2

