Plasma biomarker sample	X		
 • For participants CCI whole blood sample • Before initiation of subsequent therapy • Only if not already obtained at visit when participant discontinued study

Part C			
	Short-Term Follow-Up (30±7 Days)	Long-Term Follow-Up (90±14 Days)	Comments
Visit	801	802-X	
Relative Day within Cycle	Begins when the patient and the investigator agree that the patient will no longer continue study treatment and lasts approximately 30 days.	Begins when short-term follow-up period is complete and continues until death, study withdrawal, or the patient is lost to follow-up. In all cases, no follow-up procedures will be performed for a patient who withdraws consent/assent unless he or she has explicitly provided permission and consent/assent.	
Tissue submission from tumor biopsy obtained after progression	X		Optional Only for patients on study treatment at least 6 months
Collection of poststudy anticancer treatment	X	X	Telephone assessment is acceptable. Details of subsequent anticancer treatment (including radiotherapy, surgeries, systemic, and locoregional therapies including start/stop dates)
Survival assessment	X	X	Telephone assessment is acceptable

Abbreviations: CT = computed tomography; CTCAE = Common Terminology Criteria for Adverse Events; MIBG = metaiodobenzylguanidine; MRI = magnetic resonance imaging; PET = positron emission tomography.

Continued Access Schedule of Activities for Part C

Part C			
Visit	Study Treatment	Follow-Up	Notes
	501-5XX	901	
Procedure			
AE collection/CTCAE grading	X	X	
 • Per CTCAE Version 5.0 • Collect all AEs/SAEs • Per standard of care, monitor vital signs and perform standard laboratory tests (hematology, chemistry, and pregnancy testing) • See Section 6.7.1.1 and Section 10.2, Appendix 2
Administer abemaciclib	X		
Administer temozolomide	X		See Section 6.1
Administer irinotecan	X		Continuation on chemotherapy beyond Cycle 12 will be up to the investigator's discretion and the individual patient's situation
Administer dinutuximab	X		
Administer GM-CSF	X		

Abbreviations: AE = adverse event; CTCAE = Common Terminology Criteria for Adverse Events; GM-CSF = granulocyte macrophage colony-stimulating factor; SAE = serious adverse event.

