#### 7.4.2.5. Therapies After Study Treatment Discontinuation

The numbers and percentages of patients receiving anticancer therapies following study treatment discontinuation will be summarized. As appropriate, therapies will be summarized overall and by category.

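### Protocol 7.2 takes out of the study any Part C patient who joins another investigational study, which conflicts with the survival and later-therapy follow-up scheduled for Part C

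*Protocol*

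**What the plan says.** **Protocol 7.2**, on withdrawal from the study, is mandatory in wording. Its first bullet is "enrollment in any other clinical study involving an investigational product" (it also covers other medical research judged incompatible). Nothing confines it to the treatment period. It closes with "Participants discontinuing from the study prematurely for any reason should complete AE and other safety follow-up".

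**Protocol 7.1** lists "enrollment in any other clinical trial involving an investigational product" among the possible reasons to stop investigational product. Its closing sentence keeps AE and other follow-up procedures in general, not only safety follow-up.

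**Protocol 1.3.2, posttreatment schedule for Part C**, says that long-term follow-up "continues until death, study withdrawal, or the patient is lost to follow-up". At Visit 801 and at long-term visits 802-X it schedules "Survival assessment" and the collection of later treatment: "Details of subsequent anticancer treatment (including radiotherapy, surgeries, systemic, and locoregional therapies including start/stop dates)". Telephone contact is accepted for both. Restaging is due at each long-term visit while there is no progressive disease (PD).

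**SAP 7.4.2.5** states: "The numbers and percentages of patients receiving anticancer therapies following study treatment discontinuation will be summarized". SAP 7.2.3 tabulates all deaths. SAP 7.9 builds a participant flow on study discontinuation.

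**The concern.** The same event appears twice: once as a reason to stop drug (7.1) and once as a reason to leave the study (7.2). The second has a consequence that the first does not. A child who progresses, stops study treatment and enters another trial has to be withdrawn from the study, and that withdrawal ends long-term follow-up.

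The loss is informative. It falls mainly after progression, when the risk of death is higher than in the mixed group still followed, many of whom are progression-free. A survival curve that censors these patients treats them as having the average risk of those who remain. The subsequent-therapy record also stops where the next line is investigational, although the schedule was written to collect it.

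**Working it through.** **Step 1: the passages side by side.**

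| Question | Section 7.1 | Section 7.2 | Part C schedule |
|---|---|---|---|
| What does joining another study end? | Investigational product | Study participation | (not addressed) |
| What is still collected? | AE and other follow-up procedures | AE and other safety follow-up | Survival and later therapy at 801 and 802-X |
| When does collection end? | (not addressed) | (not addressed) | Death, study withdrawal or loss to follow-up |

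Taken literally, 7.2 triggers the study-withdrawal endpoint of the schedule. Protocol 8.3 and 8.3.1 give no backstop. After a participant leaves the study, investigators need not seek events, and a death they happen to learn of is notifiable only if thought related. Deaths from progression would therefore be missed.

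**Step 2: which outputs depend on the lost data.**

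- Deaths (SAP 7.2.3): deaths after removal are missing.
- Later therapies (SAP 7.4.2.5): details from the investigational line onward are missing.
- Participant flow (SAP 7.9): a completer has died on study or is in follow-up at the final analysis; a non-completer has withdrawn consent or is still on treatment. A patient removed under 7.2 fits neither definition.
- Restaging, and hence the progression date for DoR: lost only for a patient who leaves without PD.
- ORR: not affected. SAP 7.3.1 counts only responses before post-discontinuation therapy.
- PFS: not affected. After progression the event has already been counted. Without progression, SAP Table JPCS.7.3 already censors for new anticancer treatment.

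**Step 3: an illustration for survival.** The readable documents give no OS target for this trial, so there is no plan figure to reproduce.

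Inputs from Protocol 2.2 (the cited study of the backbone regimen): 1-year PFS 67.9% and 1-year OS 84.9%. Assumptions, not in the documents: exponential times; no death before progression; a share q of patients joins another trial 0 to 3 months after progression and is censored then; joiners have post-progression death hazard ratio r against the others.

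Progression hazard: λ = −ln(0.679) = 0.387 per year. With r = 1 and post-progression death hazard μ,

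OS(t) = [μ·exp(−λt) − λ·exp(−μt)] / (μ − λ).

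OS(1) = 0.849 gives μ = 1.333. Check: (1.333×0.679 − 0.387×0.264) / 0.946 = 0.849. Then OS(2) = (1.333×0.461 − 0.387×0.070) / 0.946 = 0.621.

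For other r, μ is solved again so that 1-year OS stays at 84.9%. Kaplan-Meier with and without the censoring was simulated in 400,000 patients per scenario; numerical integration of the same model agrees to within 0.1 point. Differences are Kaplan-Meier minus truth, in percentage points:

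| q | r | Year 1 | Year 2 | Year 3 |
|---|---|---|---|---|
| 10% | 1.0 | +0.8 | +2.0 | +2.4 |
| 30% | 1.0 | +2.6 | +6.3 | +8.1 |
| 50% | 1.0 | +4.6 | +11.2 | +14.9 |
| 30% | 0.5 | +1.7 | +4.3 | +6.1 |
| 30% | 1.5 | +3.1 | +6.9 | +8.6 |
| 10% | 0.2 | +0.1 | 0.0 | −0.1 |
| 30% | 0.1 | 0.0 | −0.4 | −1.0 |
| 30% | 0.05 | −0.3 | −1.7 | −3.4 |
| 50% | 0.05 | +0.3 | +0.9 | +1.6 |

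In the 30%, equal-prognosis row, Kaplan-Meier reads 87.5% against 84.9% at year 1 and 68.4% against 62.1% at year 2. The 1-year PFS estimate is 67.9% either way.

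**The case against.** The strongest objection is that nothing readable is estimated from these survival data. Kaplan-Meier is specified for PFS only (SAP 7.3.2.2), OS appears only in the abbreviation list, and the exploratory endpoints are redacted. A reader might infer that a planned OS analysis will be biased upward. The documents do not support that as a statement of fact, and this part of the objection stands: the bias is conditional on such an estimate being made.

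Second, follow-up may be meant to survive. Deaths are listed under safety in both documents, so the safety follow-up kept by 7.2 could include them. Study withdrawal in the schedule could mean withdrawal of consent, which the next sentence there addresses. This reading is strained. The closing sentences of 7.1 and 7.2 differ, and Section 8.3 removes any duty to look for later deaths. If it is what the sponsor intends, 7.2 should say so.

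Third, Visit 801 falls about 30 days after treatment ends and may already record the next therapy, and reasons for leaving the study are summarized. This stands in part: what is lost is mainly treatment detail and later lines.

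Fourth, the year-1 effect is small beside sampling error. With the 46 patients planned at the RP2D (SAP 6.3), the 95% half-width around 84.9% is 1.96×√(0.849×0.151/46) = 0.103, about 10 points. That is true, but the half-width describes random error only. The bias would not shrink with more patients, and it grows with follow-up time.

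**Conclusion.** The conflict is established from the text: Section 7.2 as written cuts off data that the Part C schedule asks for. The deaths summary, the later-therapy summary and the participant flow would be incomplete, as would restaging for patients who leave without PD.

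For survival, an upward bias is probable but not certain. With 10% to 50% joining and r = 1 it is +0.8 to +4.6 points at year 1 and +2.0 to +11.2 at year 2. These sizes rest on a joining share and a joiner prognosis that the documents do not state. The sign turned only at about r = 0.2 or below with 10% joining, and about r = 0.1 or below with 30%; with 50% joining it stayed upward throughout.

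A reader might also infer harm to the primary endpoint, to PFS, or to DoR in general. The documents do not support this: ORR and PFS do not use the lost data, and DoR is touched only where a responder leaves without PD.

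**What to change.** Reconcile Protocol 7.2 with the Part C posttreatment schedule:

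1. Limit the first bullet of 7.2 to participants still on study treatment, or delete it, since 7.1 already covers treatment.
2. Add one sentence: a participant in short- or long-term follow-up who enters another study stays in this study for survival and subsequent-therapy contact, and for disease status if there is no PD, unless consent or assent is withdrawn.

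This changes data collection only and leaves 7.1 as it is. The visits exist, and telephone contact is already accepted for survival and later therapy. The cost is wording in the next amendment and a few more calls. If follow-up continued in this way, the censoring shown above and its bias would not arise.
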